2.1.1 Phase I Dose Escalation

Approximately 6-9 subjects will be enrolled using a standard 3+3 design. Three to six subjects will be enrolled in each dose cohort and receive cabozantinib and pembrolizumab in accordance with the dose escalation rules described below to determine the maximum tolerated dose (MTD) and RP2D (Section 2.1.3). The dose limiting toxicity (DLT) assessment window will be 21 days (Days 1–21 of Cycle 1). If a delayed DLT is observed, the DLT assessment window may be extended after the first administration of pembrolizumab and cabozantinib for all subjects in that cohort and any subsequent dose-escalation cohorts.

Any dose-escalation stage subject who does not complete the DLT assessment window for a reason other than a DLT will be considered non-evaluable for dose escalation decisions, as well as, the MTD assessment and may be replaced by an additional subject at that same dose level.

A subject who has any component of study treatment held during the DLT assessment window for a reason other than a DLT such that administration of the next planned pembrolizumab dose is delayed by more than 7 days and/or $\geq 25\%$ of the planned cabozantinib doses are missed, will be considered non-evaluable for dose-escalation decisions and the MTD assessment and may be replaced by an additional subject at that same dose level.

| Cohort | Pembrolizumab Dose | Cabozantinib Dose |
|--------|-------------------------|-------------------|
| -1 | 200 mg IV every 3 weeks | 20 mg PO daily |
| 1* | 200 mg IV every 3 weeks | 40 mg PO daily |
| 2 | 200 mg IV every 3 weeks | 60 mg PO daily |

* Starting dose level.

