2.1.2 Definition of Dose Limiting Toxicity

Any one of the following events will be considered a DLT if it occurs during the DLT assessment window **and** is assessed by the investigator to be **likely related** to study treatment (pembrolizumab and/or cabozantinib).

- Grade \geq 3 non-hematologic, non-hepatic adverse event, with the following exceptions:
 - Grade 3 hypertension that resolves to Grade ≤ 2 with addition or adjustment of antihypertensive therapy in ≤ 7 days
 - Grade 3 fatigue that resolves to Grade ≤ 2 in ≤ 5 days
 - Grade 3 laboratory abnormalities that are asymptomatic, considered by the investigator not to be clinically significant, and that resolve to Grade ≤ 2 in ≤ 48 hours
 - Grade 3 rash that resolves to Grade ≤ 2 in ≤ 5 days with or without therapy equivalent to prednisone 10 mg/day or less
 - Grade 3 hand-foot syndrome that resolves to baseline within 3 weeks
 - Grade 3 arthralgia and/or myalgia that resolves to baseline within 3 weeks
 - Grade 3 autoimmune thyroiditis or other endocrine abnormality that resolves to Grade ≤ 2 within 3 weeks
- Grade 3 nausea, vomiting, or diarrhea lasting >72 hours despite maximal medical therapy.
- Grade \geq 4 neutropenia (ANC < 500 cells/ μ L) lasting > 7 days
- Grade \geq 3 febrile neutropenia
- \circ Grade \geq 4 anemia
- o Grade ≥ 4 thrombocytopenia, or Grade 3 thrombocytopenia associated with clinically significant bleeding
- Grade \geq 3 elevation of serum hepatic transaminase (ALT or AST).
- Grade \geq 3 elevation of serum total bilirubin.
- ALT or AST > 3 × upper limit of normal (ULN) **AND** total bilirubin >2 × ULN will require permanent treatment discontinuation.

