2.1.3 Dose Escalation Rules

Pembrolizumab will be administered at a fixed dose of 200 mg IV every 21 days on Day 1 of each cycle.

The starting dose of cabozantinib for subjects in the first cohort will be 40 mg PO once daily for 21 consecutive days of each cycle (Days 1–21). For the second cohort, the dose of cabozantinib will be 60 mg PO once daily. If the starting dose of 40mg is not tolerated (2 or more out of 6 subjects experiencing DLT), then a lower dose of 20 mg will be evaluated.

Once the DLT assessment period has passed, pembrolizumab and/or cabozantinib may be held or dose modified independent of the other agent for adverse events attributed to one but not both drugs. The Principal Investigator should be notified when this occurs.

In addition to any DLTs, other available relevant demographic, adverse event, laboratory, and dose administration data will be reviewed prior to all dose-escalation decisions.

Dose escalation will occur in accordance with the rules:

- A minimum of 3 subjects will be enrolled in each cohort.
- If none of the first 3 DLT-evaluable subjects experiences a DLT, enrollment of the next cohort may proceed.
- If 1 of the first 3 DLT-evaluable subjects experiences a DLT, the cohort will be expanded to a minimum of 6 subjects. If there are no further DLTs in the first 6 DLT-evaluable subjects, enrollment of the next cohort may proceed.
- If 2 or more of the first 6 DLT-evaluable subjects in a cohort experience a DLT, the MTD will have been exceeded and dose escalation will stop. The preceding cohort will also be expanded to a minimum of 6 subjects, unless 6 subjects have already been evaluated at that dose level.
- If the MTD is exceeded at any dose level, the highest dose at which fewer than 2 of 6 DLTevaluable subjects experience a DLT will be declared the MTD.
- If the MTD is not exceeded at any dose level, the highest dose administered in this study will be declared the maximum administered dose.
- Any dose level may be expanded in the absence of a DLT if warranted based on investigator evaluation of non-DLT adverse events, including events occurring after Cycle 1 and events observed in the expansion cohorts.
- To be considered evaluable for dose escalation, subjects must have received at least 1 dose of pembrolizumab and ≥75% of planned dosing of cabozantinib prior to completing the DLT assessment window of 21 days.

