2.1.4 Definition of Maximum Tolerated Dose (MTD)

The Maximum Tolerated Dose (MTD) is defined as the highest dose level with no more than 1 DLT reported in 6 DLT-evaluable subjects.

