2.1.5 Definition of Recommended Phase 2 Dose (RP2D)

The Recommended Phase 2 Dose (RP2D) of cabozantinib will be selected based on the clinical data and will not exceed the MTD. If < 2/6 subjects experience a DLT at 60 mg daily during dose escalation, then 60 mg daily will be considered the RP2D. If \geq 2/6 subjects experience DLTs at 60 mg daily, and \leq 1/6 subjects experience a DLT at 40 mg daily, then 40 mg daily will be considered the RP2D. The Principal Investigator, in consultation with other investigators, will continue to evaluate the safety data accumulated during the phase II dose expansion part of the study and may amend the RP2D with further experience.

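### Treatment-related stops or long holds in Cycle 1 that are not on the DLT list never enter the DLT count that sets the MTD and the default RP2D

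*Combined protocol and SAP*

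**What the plan says.** **Evaluability.** Section 2.1.1: "Any dose-escalation stage subject who does not complete the DLT assessment window for a reason other than a DLT will be considered non-evaluable". The same section makes a subject non-evaluable if treatment is held for a non-DLT reason so that "administration of the next planned pembrolizumab dose is delayed by more than 7 days", or if 25% or more of planned cabozantinib doses are missed. Sections 5.8, 8.2.2 and 8.2.5 repeat the division between a DLT and any other reason. Sections 2.1.1 and 5.8 permit replacement; 8.2.5 says that a subject who does not complete the window will be replaced. None of them separates treatment-related from unrelated reasons.

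**Exposure.** Section 2.1.3 adds that, to be evaluable, "subjects must have received at least 1 dose of pembrolizumab and" at least 75% of planned cabozantinib. It makes no exception for doses lost to toxicity.

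**DLT list.** Section 2.1.2 is a list of graded events that must be likely related to treatment. One item, for example, is "Grade 3 nausea, vomiting, or diarrhea lasting >72 hours despite maximal medical therapy". The only item that mentions discontinuation is the combined transaminase and bilirubin case.

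**Decision.** The MTD is the "highest dose level with no more than 1 DLT reported in 6 DLT-evaluable subjects". Under 2.1.5, if fewer than 2 of 6 have a DLT at 60 mg, "then 60 mg daily will be considered the RP2D".

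**Safeguards.** Before escalation, "adverse event, laboratory, and dose administration data will be reviewed prior to all dose-escalation decisions" (2.1.3), and a level may be expanded because of non-DLT events. Section 2.1.5 also says that the RP2D "will be selected based on the clinical data and will not exceed the MTD", and allows it to be amended.

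**The concern.** A subject who cannot continue because of the drugs is direct evidence about tolerability. The rules ask only whether the event is on the 2.1.2 list. If it is not, a drug-related stop is handled like a missed visit or a change of address.

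One event can decide a cohort of six. Suppose that at 60 mg one subject has a listed DLT and another has Grade 2 myocarditis. If the second is replaced, or kept as a non-DLT, and no further DLT occurs, the count is 1/6 and 60 mg is the default RP2D. If the event counted, the result would be 2/6 and the MTD would be exceeded. The RP2D is the dose carried through Phase II.

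**Working it through.** **1. Do the protocol's own management rules produce such events?**

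- *Grade 2 myocarditis.* Table 3 permanently discontinues pembrolizumab. The general DLT item starts at Grade 3, so this is not a DLT.
- *Grade 2 pneumonitis.* Table 3 and 5.4.1 require withholding, steroids and a taper of at least 4 weeks, with resumption after the taper. Onset on Day X, plus 1 day at Grade 2, plus 28 days gives Day X+29. With onset on Day 1 this is Day 30, which is 30 − 22 = 8 days after the planned Day 22 dose and over the 7-day limit. It is not a DLT.
- *Grade 2 diarrhea related to both drugs.* Table 5 requires both to be held; the DLT item starts at Grade 3.
- *Grade 3 hand-foot syndrome that resolves within 3 weeks.* It is excepted in 2.1.2, yet Table 7 requires cabozantinib to be interrupted until Grade 0 or 1.

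The last two matter only if enough cabozantinib is lost. The limit is 0.25 × 21 = 5.25 doses. Five missed doses (5/21 = 23.8%) do not cross it; six (6/21 = 28.6%) do. A six-day hold must start by Day 16. Shorter holds are unaffected.

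**2. The plan's own figures.** Table 12 uses (1−p)³ for no DLT in 3, and (1−p)⁶ + 6p(1−p)⁵ for fewer than 2 in 6. At p = 0.10, 0.20, 0.33, 0.40, 0.50 and 0.60 these give 0.729/0.886, 0.512/0.655, 0.301/0.358, 0.216/0.233, 0.125/0.109 and 0.064/0.041. All twelve cells agree with the table.

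**3. Size.** Let d be the listed-DLT rate and q the rate of the uncounted events, taken as mutually exclusive. The documents do not give q; 0.5% to 2% is an assumption. The per-subject rate that enters the rule is:

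- replaced: p = d/(1−q)
- kept as non-DLT: p = d
- counted: p = d + q

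Example with d = 0.15 and q = 0.02. Replaced: p = 0.15/0.98 = 0.1531, giving 0.769. Counted: p = 0.17, giving 0.83⁶ + 6 × 0.17 × 0.83⁵ = 0.327 + 0.402 = 0.729. The gap is about 4 points.

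Probability of fewer than 2 DLTs in 6 (gaps in percentage points, from unrounded values):

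| q | d | Replaced | Kept | Counted | Replaced − counted |
|---|---|---|---|---|---|
| 0.5% | 10% | 0.885 | 0.886 | 0.876 | 0.90 |
| 0.5% | 15% | 0.775 | 0.776 | 0.765 | 1.00 |
| 0.5% | 20% | 0.653 | 0.655 | 0.643 | 0.98 |
| 1% | 10% | 0.884 | 0.886 | 0.866 | 1.82 |
| 1% | 15% | 0.773 | 0.776 | 0.753 | 2.01 |
| 1% | 20% | 0.650 | 0.655 | 0.631 | 1.96 |
| 2% | 10% | 0.882 | 0.886 | 0.844 | 3.73 |
| 2% | 15% | 0.769 | 0.776 | 0.729 | 4.05 |
| 2% | 20% | 0.645 | 0.655 | 0.606 | 3.90 |

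If the subject is kept as a non-DLT, the gap is slightly larger, at most 4.9 points (q = 2%, d = 20%). For the escalation rule (0/3, or 1/3 then 0/3), P = (1−p)³ + 3p(1−p)⁵, and the replaced-versus-counted gaps are 0.8–0.9, 1.5–1.7 and 3.1–3.5 points for q = 0.5%, 1% and 2%.

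**The case against.** **The safeguards are real.** The review in 2.1.3 is mandatory, escalation after a clear cohort is permitted rather than required, a level can be expanded for non-DLT events, and the RP2D rests on clinical data and can be amended. In addition, 5.6.3 allows termination for adverse reactions, the DSMC reviews all SAEs (10.6.1), and 8.2.2 keeps every treated subject in the safety analyses. This stands, and it limits the severity. None of these provisions has a threshold or changes the DLT count.

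**The clearest examples concern the drug that is not escalated.** Pembrolizumab is fixed at 200 mg, so counting its events may lower the cabozantinib dose for toxicity that does not depend on it. This stands as a cost, although 2.1.2 already counts toxicity from either drug. The cabozantinib examples depend on a hold of at least six days.

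**Some details rest on one reading.** A permanent stop is not plainly a delayed dose. A subject with myocarditis who had the Day 1 infusion and 75% of cabozantinib may stay evaluable as a non-DLT. Day X+29 assumes that the taper is finished before resumption, whereas general instruction 2 of Table 3 refers to a steroid dose of 10 mg/day or less. These points affect how the subject is classified; on no reading does the event count.

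**Stronger inferences that the documents do not support.**

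- *That replacement itself flatters the dose.* It raises the evaluable DLT rate slightly, from d to d/(1−q).
- *That listed DLTs drop out when cabozantinib is missed.* The 2.1.3 bullet read alone allows this, but 2.1.1 confines non-evaluability to reasons other than a DLT.
- *That the effect is large.* This needs a much higher q. The 60% dose-reduction figure in 4.2.2.2 comes from monotherapy and is not a rate of Cycle 1 stops or long holds.

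**Conclusion.** The gap in the text is real and does not depend on any assumed rate. Likely related toxicity that is off the 2.1.2 list but stops a drug, or crosses the 2.1.1 dosing thresholds, is replaced or scored as a non-DLT, and never reaches the count behind the MTD and the default RP2D.

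The average effect on the formal rule is probably small: about 1 to 4 points in the chance of fewer than 2 in 6 if such subjects are replaced. This rests on an assumed q of 0.5% to 2% and listed-DLT rates of 10% to 20%, and it leaves out the discretionary safeguards, which would reduce the effect further.

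A reader might be drawn to a different figure: the chance that 60 mg meets the rule although at least two treated subjects had a DLT or such an event, which is 4.5% to 4.9% at q = 2%. That figure counts events among all treated subjects, sometimes more than six, so it is not the effect on the decision. Nor do the documents show that an unsafe dose would be chosen. The point is a cheap improvement to a safety rule, worth making because a single event can decide a cohort.

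**What to change.** 1. **Section 2.1.2.** Add a DLT criterion: likely related toxicity that, within the window, leads to permanent discontinuation of either drug, or to a hold required by the protocol's toxicity tables that delays the next pembrolizumab dose by more than 7 days or costs 25% or more of cabozantinib doses (6 or more of 21). Purely discretionary holds under 5.2.1.2 should not qualify, since an investigator's choice between five and six days off drug should not decide DLT status. Name the tables that apply, because 5.2.1.4 places Table 4 outside the window.
2. **All grades.** Apply the criterion to the Grade 3 exceptions as well when the dosing threshold is crossed. Otherwise a Grade 2 event with six missed doses could count while a Grade 3 hand-foot syndrome with the same loss is replaced.
3. **Section 2.1.3.** State that a subject with a DLT is evaluable whatever the exposure.
4. **Sections 2.1.1, 5.8, 8.2.2 and 8.2.5.** Limit non-evaluability and replacement to subjects without a DLT under the widened definition.

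**Cost.** One criterion using thresholds already in the protocol, matching wording in five sections, and no new data. Cohorts would be expanded, or a dose declined, slightly more often: about 1 to 4 points lower clearance under the assumed q, sometimes for pembrolizumab events unrelated to the cabozantinib dose. Table 12 keeps its numbers but must be read against the wider definition. Subjects with purely discretionary long holds would still be replaced.

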2.1.2 Definition of Dose Limiting Toxicity

Any one of the following events will be considered a DLT if it occurs during the DLT assessment window **and** is assessed by the investigator to be **likely related** to study treatment (pembrolizumab and/or cabozantinib).

- Grade \geq 3 non-hematologic, non-hepatic adverse event, with the following exceptions:
 - Grade 3 hypertension that resolves to Grade ≤ 2 with addition or adjustment of antihypertensive therapy in ≤ 7 days
 - Grade 3 fatigue that resolves to Grade ≤ 2 in ≤ 5 days
 - Grade 3 laboratory abnormalities that are asymptomatic, considered by the investigator not to be clinically significant, and that resolve to Grade ≤ 2 in ≤ 48 hours
 - Grade 3 rash that resolves to Grade ≤ 2 in ≤ 5 days with or without therapy equivalent to prednisone 10 mg/day or less
 - Grade 3 hand-foot syndrome that resolves to baseline within 3 weeks
 - Grade 3 arthralgia and/or myalgia that resolves to baseline within 3 weeks
 - Grade 3 autoimmune thyroiditis or other endocrine abnormality that resolves to Grade ≤ 2 within 3 weeks
- Grade 3 nausea, vomiting, or diarrhea lasting >72 hours despite maximal medical therapy.
- Grade \geq 4 neutropenia (ANC < 500 cells/ μ L) lasting > 7 days
- Grade \geq 3 febrile neutropenia
- \circ Grade \geq 4 anemia
- o Grade ≥ 4 thrombocytopenia, or Grade 3 thrombocytopenia associated with clinically significant bleeding
- Grade \geq 3 elevation of serum hepatic transaminase (ALT or AST).
- Grade \geq 3 elevation of serum total bilirubin.
- ALT or AST > 3 × upper limit of normal (ULN) **AND** total bilirubin >2 × ULN will require permanent treatment discontinuation.

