| | Direct bilirubin \leq ULN for subjects with total bilirubin levels $>$ | | |
| | 1.5 ULN. For subjects with Gilbert's disease $\leq 3 \text{ mg/dL}$. | | |
| AST (SCOT) and ALT (SCDT) | \leq 2.5 X ULN OR | | |
| AST (SOOT) and ALT (SOFT) | \leq 5 X ULN for subjects with liver metastases | | |
| Albumin | $\geq 2.5 \text{ mg/dL}$ | | |
| Coagulation | | | |
| International Normalized Ratio (INR) or Prothrombin Time (PT) | \leq 1.5 X ULN unless subject is receiving anticoagulant therapy as long as PT or PTT is within therapeutic range of intended use of anticoagulants | | |
| Activated Partial Thromboplastin Time (aPTT) | \leq 1.5 X ULN unless subject is receiving anticoagulant therapy as long as PT or PTT is within therapeutic range of intended use of anticoagulants | | |
| Activated Partial Thromboplastin Time (aPTT) ^a Creatinine clearance should be calculated | as long as PT or PTT is within therapeutic range of intended of anticoagulants per institutional standard. | | |

Table 1: Adequate Organ Function Laboratory Values

11. Female participants of childbearing potential should have a negative urine or serum pregnancy within 72 hours prior to receiving the first dose of study medication and should not be breastfeeding. If the urine test is positive or cannot be confirmed as negative, a serum pregnancy test will be required.

12. Female subjects of childbearing potential must be willing to use an adequate method of contraception as outlined in Section 5.5.2 – Contraception, for the course of the study through 120 days after the last dose of study medication.

Note: Abstinence is acceptable if this is the usual lifestyle and preferred contraception for the participant.

13. Male participants of childbearing potential must agree to use an adequate method of contraception as outlined in Section 5.5.2 – Contraception, starting with the first dose of study therapy through 120 days after the last dose of study therapy and refrain from donating sperm during this period.

Note: Abstinence is acceptable if this is the usual lifestyle and preferred contraception for the subject.

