| Nephritis: grading according to increased creatinine or acute kidney injury | Grade 2 Grade 3 or 4 | Withhold Permanently discontinue | • Administer corticosteroids (prednisone 1-2 mg/kg or equivalent) followed by taper. | Monitor changes of renal function |
|---|---|--|--|--|
| Neurological Toxicities | Grade 2 Grade 3 or 4 | Withhold Permanently discontinue | Based on severity of AE administer corticosteroids | • Ensure adequate evaluation to confirm etiology and/or exclude other causes |
| Myocarditis | Grade 1 Grade 2-4 | Withhold Permanently discontinue | Based on severity of AE administer corticosteroids | • Ensure adequate evaluation to confirm etiology and/or exclude other causes |
| Exfoliative Dermatologic Conditions | Suspected Stevens- Johnson Syndrome (SJS), toxic epidermal necrolysis (TEN), or Drug Rash with Eosinophilia and Systemic Symptom (DRESS) | Withhold | Based on severity of AE administer corticosteroids | • Ensure adequate evaluation to confirm etiology and/or exclude other causes |
| | Confirmed SJS, TEN, or DRESS | Permanently discontinue | | |

| All other immune- related AEs | Persistent Grade 2 | Withhold | • Based on type and severity of AE administer corticosteroids | • Ensure adequate evaluation to confirm etiology and/or exclude other causes | | | | | |
|--|---|---|--|--|--|--|--|--|--|
| | Grade 3 | Withhold or | | | | | | | |
| | | discontinue based | | | | | | | |
| | | on the type of | | | | | | | |
| | | event ^e | | | | | | | |
| | Grade 4 or | Permanently | | | | | | | |
| | recurrent | discontinue | | | | | | | |
| | Grade 3 | | | | | | | | |
| Note: Non-irAE will | Note: Non-irAE will be managed as appropriate, following clinical practice recommendations. | | | | | | | | |
| ^a AST/ALT: >3.0 to bilirubin:>1.5 to 3 | 5.0 x ULN if baseline .0 x ULN if baseline | ne normal; >3.0 to 5.0 x e normal; >1.5 to 3.0 x l | baseline, if baseline abnormal; baseline if baseline abnormal | | | | | | |
| ^b AST/ALT: >5.0 to 10.0 x baseline if t | in:>3.0 to 10.0 x ULN if baseline normal; >3.0 to | | | | | | | | |
| c AST/ALT: >20.0 x bilirubin: >10.0 x | ^c AST/ALT: >20.0 x ULN, if baseline normal; >20.0 x baseline, if baseline abnormal; bilirubin: >10.0 x ULN if baseline normal; >10.0 x baseline if baseline abnormal | | | | | | | | |

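### Eligibility, the combined ALT/bilirubin stop and the hepatic DLT grades do not share one reference point for subjects whose liver tests are abnormal at entry

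*Combined protocol and SAP*

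**What the plan says.** **Eligibility (Section 5.1.1, Table 1).** AST and ALT may be up to 2.5 x ULN, with a higher limit of "5 X ULN for subjects with liver metastases". Total bilirubin may be up to 1.5 x ULN. It may be higher if direct bilirubin is normal, and that route states no cap on the total. "For subjects with Gilbert's disease" the limit is 3 mg/dL.

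**DLTs (Section 2.1.2).** A Grade 3 or higher "elevation of serum hepatic transaminase (ALT or AST") is a DLT, and so is a Grade 3 or higher "elevation of serum total bilirubin". The event must fall within the assessment window and must be one that "is assessed by the investigator to be" likely related to treatment. The allowance for brief, asymptomatic laboratory abnormalities belongs to the item on a "non-hematologic, non-hepatic adverse event, with the following exceptions", so it does not reach liver tests.

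**Combined stop.** The last item of the same list pairs ALT or AST above 3 x ULN with "total bilirubin >2 × ULN will require permanent treatment discontinuation". Table 5 (Section 5.2.1.4.2) and the hepatobiliary guidance in Section 5.4.2 repeat the pair. None of the three has a baseline term.

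**Grading in Table 3 (Section 5.2.1.3).** The footnotes use multiples of ULN or of baseline according to the entry value. Footnote c, for example, puts Grade 4 AST/ALT above 20 x ULN "if baseline normal; >20.0 x baseline, if baseline abnormal". The column is headed CTCAE v4.0. Section 12.2 names that version but reproduces no cut-offs.

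**Use of the DLT count (Sections 2.1.3 and 2.1.4).** One DLT in the first three subjects expands the cohort to six. Two or more in six stop escalation. The MTD allows at most one in six.

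**The concern.** Three parts of the plan describe the same laboratory values and do not fit together when a subject enters with abnormal liver tests. Table 1 deliberately lets such subjects in. The combined stop is written as if everyone starts from normal. Table 3 adjusts for an abnormal start, and Section 2.1.2 does not say whether its hepatic grades do the same.

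Two things are at stake. First, an eligible subject may already hold the values at which another section requires a permanent stop. Second, the DLT count, which sets the MTD and RP2D in cohorts of three to six, depends on a grading basis that two investigators could read differently for the same result.

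**Working it through.** **1. Table 1 against the combined stop**

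- ALT/AST half: the stop begins above 3 x ULN and Table 1 admits up to 5 x ULN with liver metastases. Anyone entering above 3 and up to 5 x ULN already meets this half.
- Bilirubin half: the stop begins above 2 x ULN. The documents give no ULN, so assume 1.0 to 1.2 mg/dL. Then 3 mg/dL is 3/1.2 = 2.5 to 3/1.0 = 3.0 x ULN. It exceeds 2 x ULN for any ULN below 3/2 = 1.5 mg/dL.
- Both halves: a subject with liver metastases and Gilbert's disease can hold both values before the first dose.
- By comparison, a subject entering at 1.5 x ULN bilirubin needs a rise of more than 2/1.5 - 1 = 33% to meet the bilirubin half.

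**2. The two possible bases for a Grade 3 ALT/AST**

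Table 3 footnote b starts Grade 3 above 5.0, as a multiple of ULN or of baseline. With entry value b (x ULN), the rise needed on a ULN basis is 5/b - 1. The value to exceed on a baseline basis is 5 x b.

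| Entry value (x ULN) | Rise to Grade 3, ULN basis | Value to exceed, baseline basis |
|---|---|---|
| 5.0 | any | 25 x ULN |
| 4.9 | more than 2% | 24.5 x ULN |
| 4.0 | more than 25% | 20 x ULN |
| 2.5 (limit without liver metastases) | more than 100% | 12.5 x ULN |

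The bases disagree most for subjects near the liver-metastasis limit. Without liver metastases, ALT/AST must at least double even on the ULN basis.

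**3. Effect on dose escalation**

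The plan's own figures come first. Table 12 gives the chance of fewer than two DLTs in six as 0.89 at a 10% rate and 0.66 at 20%. Exact binomial values are 0.886 and 0.655, and all twelve cells of the table reproduce.

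Under the Section 2.1.3 rule, a dose with DLT rate p passes with probability (1-p)^3 + 3p(1-p)^5. At p = 0.10 this is 0.729 + 0.177 = 0.906, so the dose fails 9.4% of the time.

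Let s be the share of subjects with a hepatic DLT that arises only from the reference basis. The documents give no value, so s is an assumption. The combined rate is p = 1 - (1-t)(1-s), where t is the true rate.

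| t | s | p | Chance the dose fails |
|---|---|---|---|
| 0.10 | 0 | 0.100 | 9.4% |
| 0.10 | 0.02 | 0.118 | 12.5% |
| 0.10 | 0.05 | 0.145 | 17.6% |
| 0.20 | 0 | 0.200 | 29.1% |
| 0.20 | 0.02 | 0.216 | 32.6% |
| 0.20 | 0.05 | 0.240 | 37.8% |

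**The case against.** The strongest reply is that existing conditions already contain the problem.

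- The single-test DLTs are stated as grades. The only hepatic cut-offs the documents print are Table 3's, which are baseline-adjusted. Read that way, a small drift is not Grade 3.
- Every DLT must arise in the window and be judged likely related, and a pre-dose value is neither.
- Section 7.2.2 speaks of a clinically significant worsening of a pre-existing condition, which a drift of a few percent hardly fits.
- Section 5.4.2 attaches the combined stop to drug-related elevations, and Table 5 covers toxicities of both drugs or of unclear attribution.
- Exclusion 20 lets the investigator keep out a confounding laboratory abnormality.
- For Grade 3 or 4 liver tests, Tables 3 and 5 require the same action.

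Much of this stands, and it rules out several stronger readings. A reader might infer that the single-test DLTs are fixed multiples of ULN. The documents do not say so; they leave the basis unstated. A reader might infer that Day 1 values trigger the stop. They satisfy its numbers, but the attribution conditions still apply. A reader might also infer that one trivial change lowers the MTD. It cannot, because two DLTs in six are needed. Finally, the chance of fewer than two DLTs in six falls from 0.886 to 0.9^5 = 0.590 (or from 0.655 to 0.8^5 = 0.328) if one of the six is already counted. That arithmetic is right, but it presupposes the event and so does not measure how often it happens.

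The reply does not supply a rule. Relatedness and exclusion 20 are judgements, Table 1 expressly admits these values, and attribution is hardest when the baseline is already abnormal.

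**Conclusion.** The point holds as a conflict between stated rules for a limited group. Those affected are subjects with liver metastases and raised transaminases, and subjects with Gilbert's disease or raised total bilirubin with normal direct bilirubin. Two facts can be verified from the text: the combined stop has no baseline term although Table 1 admits values beyond its limits, and Section 2.1.2 leaves open whether its hepatic grades follow ULN or Table 3's baseline rule. That both stop values can be present before dosing rests on the assumed bilirubin ULN.

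The effect on escalation is modest and illustrative. With an assumed 2% to 5% of subjects affected, the failure chance for a dose with a true 10% rate rises by about 3 to 8 percentage points. The documents give no prevalence, and Phase I plans only about 6 to 9 subjects, so the real number affected may be zero. The last item in the Section 2.1.2 list is also worded as a discontinuation rule, so whether it counts as a DLT is unclear.

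**What to change.** Reconcile Table 1, the hepatic items of Section 2.1.2, the Table 3 footnotes, Table 5 and the hepatobiliary part of Section 5.4.2. For subjects with abnormal AST, ALT or bilirubin at entry, state one reference basis, ULN or baseline, that governs both the hepatic DLT grade and the combined stop. Bring the stop rule and Table 1 into agreement, and say whether meeting the combined rule is itself a DLT. The clinical team chooses the basis and the thresholds.

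The cost is protocol wording. The schedule of events already collects the screening chemistry, so no extra tests are needed.
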